#### 4 TREATMENT PLAN

### 4.1 Treatment plan

The screening/baseline evaluations are performed to determine the subject's eligibility for study participation and for determination of the baseline status. In the actual treatment period, an abdominal radical hysterectomy or minimally invasive surgery (conventional laparoscopic or robot-assisted) will be performed with pelvic lymphadenectomy (LNE) or optional sentinel lymphadenectomy during visit 3 (day 0). As diagnostic test sentinel lymph node biopsy and/or complete lymphadenectomy is recommended before radical hysterectomy to assess the lymph node status (frozen section) in order to avoid the combination of radical surgery and radiochemotherapy by abandoning the radical hysterectomy in case of lymphatic spread. Following the recent presentation of the SHAPE trial results at ASCO 2023: if a simple hysterectomy is to be considered for patients with low-risk early-stage cervical cancer meeting the SHAPE criteria (tumor < 2cm, < 10 mm depth of stromal invasion (LEEP/cone) this must already be determined before the randomization process. Simple hysterectomy has to be performed as extrafascial hysterectomy and the preparation of a max. 5mm vaginal cuff is required to ensure negative margins. Patients meeting the inclusion criteria and not fulfilling the exclusion criteria will be randomized (see section 2.6) to one of the following arms:

#### Experimental Treatment

In the standard arm, radical hysterectomy is performed as per standard technique (abdominal radical hysterectomy (Piver type 2 or 3 or Querleu & Morrow Type B or C) with salpingectomy +/- oophorectomy. Ovaries may be removed or preserved +/- transposition. Surgery includes pelvic lymph node dissection or optional sentinel lymph node biopsy (SNB) according to current guidelines in both study arms.

In the experimental arm, radical hysterectomy is performed as per standard conventional 2D/3D laparoscopic or robotic assisted technique (Querleu & Morrow Type B or C) with salpingectomy +/- oophorectomy. Ovaries may be removed or preserved +/- transposition. The following protective measures are mandatory for the minimal-invasive arm: LEEP/conization before randomization or closure of the vagina before colpotomy. Transcervical manipulators are not permitted. Use of uterus manipulators/ cervical adapter (without transcervical device) are allowed only after LEEP/conization. Meticulous dissection of pelvic (sentinel) lymph nodes including use of endobags and avoiding the dissemination of cancer cells will be implemented (tumor hygiene).

Due to the positive results of the SHAPE trial presented at ASCO 2023, in both arms simple hysterectomy can be considered for patients with low-risk early-stage cervical cancer (SHAPE-criteria: tumor < 2cm, < 10 mm depth of stromal invasion (LEEP/cone) BUT has to be determined BEFORE randomization. Surgery can be performed including removal of the sentinel lymph nodes following the concept of sentinel lymph node biopsy (SNB) and according to the current guidelines. Simple hysterectomy has to be performed as extrafascial hysterectomy and the preparation of a max. 5mm vaginal cuff is required to ensure negative margins.

The Follow-Up period begins 1 month (+/- 7 days) after surgical treatment and will take a minimum of 5 years per patient.

### 4.1.1 Surgical treatment

A pelvic examination will be performed under anesthesia, to verify the clinical stage. The operative treatment starts with injection of tracer (99mTc and blue dye and/or ICG and/or blue dye) subepithelially in the uterine cervix, and SLN biopsy with frozen section which is recommended for all patients to allow (secondary) pathological ultrastaging. For laparoscopic treatment an intrauterine manipulator is not allowed. The abdomen is then entered according to the

result of the randomization. After extirpation of the sentinel nodes, pelvic lymphadenectomy is performed according to current guidelines followed by the radical hysterectomy. Ovaries may be removed or preserved +/- transposition. In case of leaving the ovaries *in situ* it is recommended that the salpinges are extirpated. If surgery is performed by laparoscopy (conventional or robotic assisted can be chosen according to the discretion of the surgeon) the lymph nodes are retrieved via specimen retrieval bags and the hysterectomy specimen is retrieved via the vagina. Closure of the vagina to cover the cervix (vaginal cuff) before colpotomy is mandatory in the laparoscopic group unless LEEP/conization has been performed before randomization. Transcervical manipulators are not permitted. Use of uterus manipulators/ cervical adapter (without transcervical device) are allowed only after LEEP/conization (with clinical R0 resection).

If a simple hysterectomy is to be considered for patients with low-risk early-stage cervical cancer meeting the SHAPE criteria (tumor < 2cm, < 10 mm depth of stromal invasion (LEEP/cone) this must already be determined before the randomization process. The technique of simple hysterectomy follows the classical procedure either in the standard arm (abdominal) or experimental arm (laparoscopy) according to randomization result. Simple hysterectomy has to be performed as extrafascial hysterectomy and the preparation of a max. 5mm vaginal cuff is required to ensure negative margins.

#### Definition of radical hysterectomy

The surgical treatment is based on the valid local guidelines for the treatment of cervical cancer. The extend of surgery should be linked to the classification of Querleu & Morrow and/or Piver.

### Definition of anatomical boundaries for pelvic (and paraaortic) lymphadenectomy

The lymphadenectomy is defined as resection of all fatty tissue and lymph nodes in the areas according to Marnitz et al. (Figure 2). The extent of lymphadenectomy includes for the pelvis the common iliac (2), external iliac (3), internal iliac nodes (5) and obturator fossa (4). If a paraaortic lymph node dissection is necessary the paraaortic lymphadenectomy includes the paracaval, interaortocaval and paraaortal tissue (1) up to the renal veins.

[figure not shown]

Figure 2: Areas of lymph node dissection

### 4.1.2 Sentinel Node Biopsy procedure

The surgical procedure starts with marking, identification and dissection of the sentinel lymph nodes and should be performed described as below regardless the treatment arm.

Cervical injection of isotope (99mTc), will be performed on the day before (long protocol) or on the morning of surgery (short protocol). The report provided by the nuclear physician will detail number and location of SLN according to the Marnitz classification. Intracervical injection for sentinel lymph node detection with blue dye and/or ICG will be performed directly before operation.

The surgical access will be obtained according to the result of the randomization (laparoscopy or open surgery). Once the nodal pelvic and para-aortic areas are visible (especially after adhesiolysis), the areas are explored with the Gammaprobe to detect radio-labelled SLN. If ICG is used an endoscope with fluorescence imaging is mandatory (i.e. FireFly®). The "hot" and/or "coloured nodes" are biopsied by a specific incision. Laparoscopic extraction of the SLN must be performed with an extraction bag or through a port to avoid port-site contamination. A correlation should be performed with the result of the lympho-scintigraphy or SPECT/CT. Radioactivity and colour of the nodes is verified again after extraction. Number and location of SLN has to be noted on histopathological examination requirement form and surgical report according to the classification of Marnitz. SLN are given to the pathologist for frozen section (FS).

### Safety algorithm of sentinel lymph node biopsy

All the preoperative lympho-scintigraphy or SPECT/CT mapped nodes must be harvested. All suspicious nodes must be removed. In case of unilateral pelvic non-detection of SLN, a complete lymphadenectomy on that site should be performed. Inspection of the nodal areas during the radical /simple hysterectomy (especially parametria) is necessary. Nodes macroscopically suspect of metastatic disease are defined as such regardless of ICG uptake or technetium/Patent Blue positivity, and must be resected and noted in the study file.

### Pathology of sentinel lymph nodes - frozen section

SLNs will be cut in half along their long axis. One of the two parts will be examined in FS in one level after staining with Hematoxylin-Eosin (HE). The other half of the node will be immediately fixed for the definitive examination.

### Definitive examination and ultrastaging

Histological examination of all SLNs will be performed after staining with hematoxylin-eosin (HE) on sections of 200 microns. Negative SLNs with HE, will undergo immunohistochemistry (IHC) with anti-cytokeratin AE1-AE3.

Non-sentinel lymph nodes will be examined after staining with HE. Histological analyses will be carried out systematically in the same center by the same pathologist expert for SLN biopsy.

The isolated tumor cells are defined as < 0.2 mm, micrometastases, between 0.2 mm and 2 mm and macrometastases as > 2 mm.

## 4.1.3 Sentinel Lymph Node algorithm

The sentinel lymph node algorithm includes;

- Intracervical injection of ICG and/or blue dye and Technetium-Isotope (99mTc)
- Planar lympho-scintigraphy or SPECT/CT with report of number and location of SLN according to the Marnitz classification if available at the study center

- Removing of SLN according to the result of the lympho-scintigraphy or SPECT/CT or as visualized by ICG/blue staining
- Using extraction bag for SLN in laparoscopic approach
- Resection of all macroscopic suspicious lymph nodes regardless of mapping success or not

### 4.2 Duration of Treatment

The duration of the surgical intervention per participant depends on individual circumstances and will take between 150 and 300 minutes followed by a Follow-Up period of at least 60 months (5 years).

# 5 STUDY PROCEDURES / EVALUATIONS

# 5.1 Study Calendar

Study phase	Screening/ Baseline		Treatment	Follow-up						
Procedures	Visit 1 – Screening (Day –28 to –1	Visit 2 – Enrollment (Day -28 to - 1)	Visit 3 – Surgery (Day 0)	Visit 4 – FU 1 (1 month +/- 7 days)	Visit 5 – FU 2 (6 months +/- 3 weeks)	Visit 6 – FU 3 (1 year +/- 1 month)	Visit 7 – FU 4 (2 years +/- 1 month)	Visit 8 – FU 5 (3 years +/- 1 month)	Visit 9 – FU 6 (4 years +/- 1 month)	Visit 10 – FU 7 (5 years +/- 1 month)
Informed Consent	Х									
Eligibility Criteria	х									
Pregnancy Test 	х									
Demographics and medical history	х									
Randomisation 		х								
Record surgical procedure performed and localization of sentinel lymph node			х							
Record intra-operative complications 			х							
Pap smear from cervix 		X 	X 							
Urine sample 		X 	X 							
Length of stay				х						
Record post-operative complications				х	х	х				
Record pathology of the uterus				x						
Record adjuvant treatment						х				
Collection of blood for biobank 			х							
Collection of tumor material (Hysterectomy and lymph nodes) specimens) 			х							

Quality of life questionnaires 	х		х	х	х	х	х	х	x
Lymphatic side effects 	Х		Х	Х	Х	Х	Х		
Follow-up care (according to national guidelines)			X	X	х	X	x	х	X
Record if recurrence				Х	х	Х	х	х	Х
Serious Adverse Events		X	Х	Х	Х				

 Serum pregnancy testing at screening for women of childbearing potential only; Randomisation only after completed quality of life questionnaires;  According to Rosenthal (Appendix 12.1); Biomaterials will only be collected if separate Informed Consent is signed by the patient; These assessments can be carried out either at visit 2 (enrollment) or visit 3 (surgery) EORTC QLQ-C30 + EORTC QLQ-CX24, EuroQol EQ-5D-3L + SAQ (Appendix 0); Lymphatic side effects according to the CTCAE 3.0 and LYMQOL Questionnaire (Appendix 12.2). The LYMQOL needs to be completed only if the patient reports that she has lymphedema

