# STUDY SYNOPSIS

Title of study	A randomized clinical trial comparing laparoscopic or robot-assisted radical/simple hysterectomy versus abdominal radical/simple hysterectomy in patients with early-stage cervical cancer
Short term	G-LACC (German-funded Laparoscopic Approach to Cervical Cancer)
Responsible investigator	[name]. [name] Hannover Medical School Department of Gynecology and Obstetrics [name] Germany
Study design	Interventional, multicenter, open-label, randomized, controlled non-inferiority trial
Subject population	Female patients with operable early-stage cervical cancer: International Federation of Gynecology and Obstetrics (FIGO) stage IA2 - IB2 < 4cm and a histologic subtype of squamous-cell carcinoma, adenocarcinoma, or adenosquamous carcinoma
Participating study sites	20–30 trial sites in Germany and other countries
Number of subjects	To be enrolled: n = 756 women (378 women per treatment arm) The study is event-driven, at least 45 primary endpoint events need to be observed to demonstrate the non-inferiority of laparoscopic or robot-assisted radical/simple hysterectomy compared to abdominal radical/simple hysterectomy with regard to disease-free survival (DFS) using a pre-defined non-inferiority margin of 2.3 for the hazard ratio (HR). To be assessed for eligibility: n = 2100 women
Objectives	Primary Objective To investigate the oncologic safety of laparoscopic or robot-assisted radical/simple hysterectomy compared to abdominal radical/simple hysterectomy using pre- specified surgical techniques and qualitative standards and to demonstrate the non-inferiority with a non-inferiority margin of 2.3 for the hazard ratio (HR) for disease free survival (DFS), defined as the time from randomization to disease recurrence or death from any cause (whichever occurs first). Secondary Objectives

	To evaluate overall survival, disease recurrence, quality of life, complications and treatment-associated morbidity, treatment costs and cost effectiveness.
Inclusion and exclusion criteria	Inclusion criteria
	Histologically confirmed primary adenocarcinoma, squamous cell carcinoma or adenosquamous carcinoma of the uterine cervix
	• Patients with FIGO stage IA2, IB1 or IB2 disease (< 4 cm)
	• Patients undergoing radical hysterectomy according either to Type II or III (Piver Classification) or to Type B or C (Querleu and Morrow classification)
	OR

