### Quality of life including lymphatic side effects

Health Related Quality of Life (HRQoL) will be assessed by using validated questionnaires comprising EORTC QLQ-30, EORTC QLQ-CX24 EuroQoL EQ-5D-3L. Sexual activity will be assessed by using the Sexual Activity Questionaire (SAQ). Additionally, lymphatic side effects will be assessed by the investigator using CTCAE 3.0 and by the patient using the LYMQOL questionnaire. HRQoL and lymphatic side effect assessments will be conducted over the whole course of the trial (see sections 5.3.11 and 5.3.12 and Appendix 0 and 12.2).

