# 5.2.4 Follow Up Visits

The Follow Up period begins with visit 4 (1 month after surgery +/- 7 days) and lasts for at least 5 years. Completed assessments will be collected either in connection to the visit at the clinic, electronically (eCRF) or per conventional mail.

The following evaluations are performed during the Follow-up period:

- Length of stay (visit 4)
- Recording of post-operative complications (visits 4–6)
- Recording of pathology of the uterus (visit 4) \*
- Record of adjuvant treatment (if applicable, visit 6)
- Quality of life questionnaire (visits 4–10)
- Lymphatic side effects questionnaire (visits 4–8)
- Record of recurrence (if applicable, visits 5–10)
- Adverse events (visits 4–8)

\* Tumor size assessment in case of prior LEEP/cone excision should be estimated according to the College of American Pathologists (CAP). In providing the final tumor dimensions, the measurements in any prior specimens, for example LEEP/cone excision, will need to be taken into account. Although it may overestimate the maximum horizontal extent, it is recommended to add together the maximum lateral measurements in different specimens when calculating the final horizontal extent. For a detailed description of the assessments, please see section 5.3.

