## LYMQOL

The Lymphoedema Quality-of-Life Questionnaire (LYMQOL) is a validated disease-specific tool which was developed to measure the impact of lymphoedema on patients' quality of live. The LYMQOL needs to be completed only if the

patient reports that she has lymphedema. The LYMQOL questionnaire assesses the impact of lymphoedema on several aspects of the patient's life and covers four domains (symptoms, body image/appearance, function and mood).

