## 7.1.3 Secondary endpoints

Overall survival (OS) will be analyzed in line with the primary analysis of the primary endpoint.

Data for other secondary endpoints will be summarized by treatment groups, compared with appropriate statistical tests adjusted in line with the primary analysis of the primary endpoint.

Absolute and relative frequencies of serious adverse events (SAEs) will be displayed for the whole population and separately for each treatment group and comparisons between groups using Chi-squared tests will be performed and assessed descriptively.

Analyses of DFS and OS in relevant subgroups will also be performed for the following subgroups:

- tumor size (<2cm vs 2-<4 cm)
- sentinel node mapping only (yes vs no)
- radical vs simple hysterectomy (SHAPE criteria)

- anticipated type of minimally invasive surgery (laparoscopic vs robot-assisted)
- histological type (squamous cell carcinoma vs. adenocarcinoma, adenosquamous carcinoma)
- grading (G1-2 vs G3)
- center

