#### 9.3.2 Sub-Committee on Quality of Life

Women of the G-LACC trial will be requested to complete a variety of questionnaires as part of the study protocol. For more information on the content of these questionnaires, please refer to section 5.3.11. The Sub-Committee on Quality of Life will monitor the data acquisition and interpret the corresponding results in close consultation with the Trial Steering Committee. Patient-reported out-come-measures serve to estimate the occurrence and severity of delayed effects associated with both the standard and the experimental treatment arm. Consequently, it becomes crucial to oversee the data acquisition and to provide these affected women with treatments that minimize the risk of long-term side effects.

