#### EORTC QLQ-CX24

# EORTC QLQ - CX24

Patients sometimes report that they have the following symptoms or problems. Please indicate the extent to which you have experienced these symptoms or problems, please answer by circling the number that best applies to you.

Du	ring the past week:	Not at all	A little	Quite a bit	Very much
31.	Have you had cramps in your abdomen?	1	2	3	4
32.	Have you had difficulty in controlling your bowels?	1	2	3	4
33.	Have you had blood in your stools (motions)?	1	2	3	4
34.	Did you pass water/urine frequently?	1	2	3	4
35.	Have you had pain or a burning feeling when passing water/urinating?	1	2	3	4
36.	Have you had leaking of urine?	1	2	3	4
37.	Have you had difficulty emptying your bladder?	1	2	3	4
38.	Have you had swelling in one or both legs?	1	2	3	4
39.	Have you had pain in your lower back?	1	2	3	4
40.	Have you had tingling or numbness in your hands or feet?	1	2	3	4
41.	Have you had irritation or soreness in your vagina or vulva?	1	2	3	4
42.	Have you had discharge from your vagina?	1	2	3	4
43.	Have you had abnormal bleeding from your vagina?	1	2	3	4
44.	Have you had hot flushes and/or sweats?	1	2	3	4
45.	Have you felt physically less attractive as a result of your disease or treatment?	1	2	3	4
46.	Have you felt less feminine as a result of your disease or treatment?	1	2	3	4
47.	Have you felt dissatisfied with your body?	1	2	3	4
	Please go on to the next page		×.		

Du	ring the past 4 weeks:	Not at all	A little	Quite a bit	Very much
48.	Have you worried that sex would be painful?	1	2	3	4
49.	Have you been sexually active?	1	2	3	4
	wer these questions only if you have been ally active during the past 4 weeks:	Not at all	A little	Quite a bit	Very much
50.	Has your vagina felt dry during sexual activity?	1	2	3	4
51.	Has your vagina felt short?	1	2	3	4
52.	Has your vagina felt tight?	1	2	3	4
53.	Have you had pain during sexual intercourse or other sexual activity?	1	2	3	4
54.	Was sexual activity enjoyable for you?	1	2	3	4
©QLQ	-CX24 Copyright 2003 EORTC Quality of life Group. All rights reserved. (phase III module)				

[figure not shown]

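### LYMQOL is completed only by women who report lymphoedema, so a between-arm test of its scores is not protected by randomisation; it should be descriptive, with the arm comparison based on the QLQ-CX24 lymphoedema item

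*Protocol*

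**What the plan says.** All references are to the Protocol.

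- **Who completes LYMQOL.** Footnote 7 of the study calendar (5.1) states: "The LYMQOL needs to be completed only if the patient reports that she has lymphedema". The LYMQOL paragraph in 5.3.13 repeats the rule, so it is not a stray footnote.
- **Its role.** LYMQOL belongs to the secondary endpoint on quality of life including lymphatic side effects. Section 2.3.2 says that "lymphatic side effects will be assessed by the investigator using CTCAE 3.0 and by the patient using the LYMQOL questionnaire".
- **The planned comparison.** Section 7.1.3 treats the secondary endpoints other than overall survival together. They are to be summarised by treatment group and "compared with appropriate statistical tests adjusted in line with the primary analysis of the primary endpoint". LYMQOL is not exempted.
- **The purpose.** Section 9.3.2 says: "Patient-reported out-come-measures serve to estimate the occurrence and severity of delayed effects associated with both the standard and the experimental treatment arm".
- **Measures without the restriction.** QLQ-CX24, which 5.3.12 has all patients complete, contains a lymphoedema scale and asks "Have you had swelling in one or both legs". CTCAE version 3.0 grading by the investigator (5.3.13, Appendix 12.2) is not limited to women who report lymphoedema. Lymphoedema is also on the list of post-operative complications (5.3.7).

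**The concern.** Lymphoedema that appears after surgery arises after randomisation and is something the two techniques may cause at different rates. The protocol treats it that way itself, as a listed complication, a graded toxicity and a quality-of-life scale. LYMQOL scores during follow-up will therefore exist only for women selected by an outcome of treatment. A test between arms on those scores compares women with lymphoedema in one arm with women with lymphoedema in the other. These are not the groups that randomisation made comparable. The trial is open-label, so the self-report that triggers the form is also made with knowledge of the operation.

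Two misreadings follow. If one technique causes more lymphoedema of the same severity, the LYMQOL comparison shows no difference. If it causes additional mild cases, they pull down its average and it looks better. Few women may contribute scores, so the comparison would also be imprecise.

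**Working it through.** The protocol gives no incidence, mean, standard deviation or sample size for LYMQOL, so there is no stated figure to reproduce. The point is structural, and the arithmetic below only illustrates it.

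**Inputs**

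- From the protocol: 378 women per arm (7.2); four answer categories from 'not at all' to 'a lot' on the LYMQOL form.
- Assumed: coding 1 to 4, higher being worse; 10% to 40% of women per arm reporting lymphoedema; arm B has the same cases as arm A (mean 2.2) plus extra cases with mean *m*. The illustration concerns items about leg swelling only, where 1 is a sensible value for a woman without swelling.

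**Formulas**, with pA and pB the proportions affected:

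- Affected women only: A = 2.2; B = [pA × 2.2 + (pB − pA) × m] / pB.
- All women: each arm = p × (mean among affected) + (1 − p) × 1.

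**Worked case**, pA = 10%, pB = 20%, m = 1.5:

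- Affected only: B = (0.10 × 2.2 + 0.10 × 1.5) / 0.20 = 0.37 / 0.20 = 1.85, against 2.20 in A. B looks 0.35 better.
- All women: A = 0.10 × 2.2 + 0.90 = 1.12; B = 0.20 × 1.85 + 0.80 = 1.17. B is 0.05 worse.

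**Range** (differences are B minus A; negative favours B)

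| pA / pB | m | Affected only: A, B | Difference | All women: A, B | Difference |
|---|---|---|---|---|---|
| 10% / 20% | 1.5 | 2.20, 1.85 | −0.35 | 1.12, 1.17 | +0.05 |
| 20% / 30% | 1.5 | 2.20, 1.97 | −0.23 | 1.24, 1.29 | +0.05 |
| 20% / 40% | 1.3 | 2.20, 1.75 | −0.45 | 1.24, 1.30 | +0.06 |
| 10% / 20% | 2.2 | 2.20, 2.20 | 0.00 | 1.12, 1.24 | +0.12 |
| 10% / 20% | 2.6 | 2.20, 2.40 | +0.20 | 1.12, 1.28 | +0.16 |

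Over rates of 10/20, 15/25, 20/30 and 20/40% with m from 1.3 to 1.8, the affected-only difference favours B by 0.13 to 0.45, while the all-women difference is against B by 0.03 to 0.16. With equally severe extra cases (m = 2.2) a doubled incidence is invisible among affected women. With more severe ones (m = 2.6) the direction is correct.

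**Precision.** The standardised difference detectable with 80% power at two-sided 5% is (1.96 + 0.84) × √(2/n), with n per arm.

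- 10% reporting: n = 378 × 0.10 ≈ 38, difference 0.64.
- 40% reporting: n = 378 × 0.40 ≈ 151, difference 0.32.
- All 378 per arm: difference 0.20.

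**The case against.** The strongest reply has four parts.

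1. **The protocol nowhere says that LYMQOL is tested among completers only.** Section 7.1.3 is one general sentence, and an analysis set for one questionnaire is normally left to the SAP, which is not at hand. This stands in part: a reader might infer that the sponsor has chosen a completers-only test, and the text does not say so. But the protocol fixes both the restricted collection and a comparison without exception. Followed as written, with scores only from women who report lymphoedema, the two lead to that test.

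2. **The restriction is correct use of the instrument.** The form states that it was designed and validated for patients with leg oedema, and many items refer to the swollen leg. This stands. The fault is pairing the restriction with a test between arms.

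3. **Lymphoedema is already compared in all women.** This stands, and it limits the point. A reader might infer that the treatment effect on the whole secondary endpoint could reverse. The documents do not support that: QLQ-CX24, CTCAE grading and the complication record can each show an excess, so only the LYMQOL result could mislead.

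4. **The reversal rests on assumed figures.** This also stands. It needs extra cases that are milder, and nothing in the protocol says they will be.

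A tempting repair is to score every unaffected woman 'not at all' and analyse LYMQOL in all women. It does not fit the whole instrument. Questions 16 to 21 cover sleep, concentration and mood in general and are taken from QLQ-C30; question 22 rates overall quality of life from 0 to 10. A woman without lymphoedema may sleep badly or feel low, so fixed values there would be invented data.

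**Conclusion.** The concern holds for LYMQOL alone. A between-arm test on completed LYMQOL forms is not protected by randomisation. It can conceal a difference in incidence, and it can favour the arm with more lymphoedema when that arm's extra cases are milder. That it will do so cannot be claimed. The conclusion about randomisation rests only on the completion rule and on lymphoedema being a post-operative outcome, both in the protocol. The sizes (0.13 to 0.45 points in the wrong direction; 38 to 151 women per arm at 10% to 40% reporting) rest on assumptions.

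The weight is moderate: one instrument within one secondary endpoint. The primary analysis of disease-free survival is untouched. The change should be made, but the trial's main conclusion does not depend on it.

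**What to change.** In sections 2.3.2 and 7.1.3, and in the SAP, state that:

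- LYMQOL is summarised descriptively among women who report lymphoedema, with the number contributing per arm and visit, and without a between-arm test;
- the randomised patient-reported comparison of lymphoedema uses the QLQ-CX24 lymphoedema item in all randomised women, alongside CTCAE grade.

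The completion rule can stay. Women without lymphoedema should not be given imputed LYMQOL scores.

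The cost is a sentence or two and no new data, because QLQ-CX24 is already completed by all patients. The one loss is a formal LYMQOL test, which could not have been read as an effect of treatment.

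In the same edit, the visits for lymphatic assessments need to be reconciled: 5.1 and 5.2.4 have them through visit 8, while 5.3.13 has them through visit 10.
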